6.2. Recruitment and enrolment

The recruitment of potential subjects will only commence once authorisation and approval from EC. The recruitment period from first subject enrolled to last subject enrolled is expected to be approximately two month.

Recruitment method	Sites	Coloplast database
Potential candidates		
First contact		
Screenings visit (V0)	 the investigation and review the inclusion reconsider his/her participation at V0, th hours before deciding on participation. I the clinical investigation, a Baseline Vis same day as the screening visit. The screening can be performed at the screening can be performed can be performed	e Principal Investigator or delegate will introduce n and exclusion criteria. If the subject wishes to e subject has the right to wait a minimum of 24 f the subject hereafter decides to participate in it (V1) will be scheduled unless performed the site or as a phone call. If the subject does not exclusion criteria, this will be registered at the
Baseline visit (V1)		

Table 3: Overview of the recruitment process

6.2.1. Informed consent process

Written informed consent is obtained from all subjects participating in the investigation after thorough written and verbal information. The information is given by the PI or designee in the subjects' native non-technical language. Each subject will be fully informed about the aim of the investigation, procedures, potential risks, or inconveniences and/or expected benefits, and all anticipated adverse device effects. The subject will receive both written and verbal information to ensure that the subject understands what was read and explained and can freely agree to participate in the investigation. The subject will, beforehand, also be informed about the possibility of bringing a companion to any subsequent visits. The verbal information must be given in reasonable quite surroundings.

The subject has the right to wait a minimum of 24 hours before deciding on participation and will be informed that their participation is voluntary and that they may leave the investigation at any time, without this having any influence on their further treatment.

The informed consent signature form includes personally dated signatures of the subject and the PI or designee (must be a medical doctor by profession) will be responsible for conducting the informed consent process. A copy will be provided to the subject.

If new information is to be given during the investigation, sponsor will inform the PIs, and the new information is given to the subjects by the PI. If new information becomes available that can significantly affect a subject's future health and medical care that information will be provided to the subject in written form. The CM is responsible for writing the information and providing the approved Subject Information and Consent Form to PIs that will further provide it to the subjects. If applicable, all affected subjects shall be asked to confirm their continuing informed consent in writing.

This procedure also applies to informed consent obtained from a subject's legal representative. The procedure cannot waive the subjects' legal rights.

6.2.2. Point of enrolment

A subject is considered enrolled in the investigation at the time of consent. Prior to any clinical investigation related procedures are undertaken, the subject signs and dates the informed consent form. The expected duration for each subject is described in section 5.1.

6.2.3. Subject screening and randomization failures

Subjects that have signed the informed consent form but fail to comply with the eligibility criteria are considered screening failures. A screening failure will be replaced by a new subject if the subject is not randomized.

If a subject is randomized by mistake (e.g., if the PI realizes that the subject is not eligible after the subjects has been randomized), this is considered a randomization failure. If the subject has not been treated and has no data registered on the primary endpoint the subjects can be replaced by a new subject if the new subject can complete the investigation within timelines (before last subjects last visit and within visit windows).

6.2.4. Subject withdrawal criteria

The subject is allowed to withdraw from the investigation at any time for whatever reason without any consequences for their future treatment outside the clinical investigation. The Investigator may withdraw a subject from the investigation at any time if they judge it to be the subject's interest.

The investigator must withdraw a subject from the investigation due to:

- Noncompliance with the CIP impacting the scientific integrity of the investigation.
- If subject's safety and wellbeing is compromised by further participation.
- Subjects lost to follow-up. At least three documented attempts will be made to verify subjects lost to
 follow-up. If, after these attempts are made, and there is still no response, the subject will be withdrawn from the clinical investigation.

6.2.5. Subject Identification and Confidentiality

Subjects will be identified on the Case Report Form (CRF), and any other document transmitted to the sponsor by the PI or clinical site staff, by a unique identification number.

The PI for each clinical investigation site will maintain, as part of the investigational file, a list identifying all subjects entered the clinical investigation.

7. Procedures

7.1. Transanal irrigation set-up

Subjects are allowed to lay down during the insertion of the rectal catheter (both the investigational device and the comparator device). After insertion the rectal catheter the subjects should move to a toilet chair to complete the TAI procedure. When the TAI procedure is completed the subjects can move to the toilet to empty their bowel.

7.2. Clinical investigation-related procedures

Visit 0 - Screening visit and study information:

- Introduction to the investigation and review of Subject Information Form/Informed Consent Form
- Scheduling V1 unless performed the same day as V0
- Register the potential subject on the pre-screening log.

Visit 1 - Inclusion and TAI procedure

- Introduction to the investigation reviewed and confirmed by subject
- Sign Informed Consent Form
- Allocation of subject ID number
- · For female subjects of childbearing potential urine pregnancy dipstick must be done
- Check of inclusion and exclusion criteria
- Obtain relevant medical history (assessed by PI)
- Collection of baseline data (see section 5.5)
- Randomization electronically in

Was it possible to perform the TAI procedure?

- Complete adverse events, device deficiencies, vigilance or protocol deviation forms, if applicable (see section 5.3.4)
- Complete Electronic Case Report Form (eCRF) incl. additional comments in comment field (if relevant)
- Schedule V2 (up to 14 days after V1)

Visit 2 - TAI procedure

Ensure the subjects well-being and that the subject is still comfortable to participate in the clinical investigation.

 Review for safety adverse events/serious adverse events/adverse device effects/protocol deviations/device deficiency

as it possible to perfe	orm the TAI proced	lure?		
omplete adverse ever	nts, device deficien	cies, vigilance form	or protocol deviation fo	rms, if applicable
	mplete adverse ever	mplete adverse events, device deficien	is it possible to perform the TAI procedure? mplete adverse events, device deficiencies, vigilance form mplete eCRF, including termination form and additional co	is it possible to perform the TAI procedure? mplete adverse events, device deficiencies, vigilance form or protocol deviation fo mplete eCRF, including termination form and additional comments in comment fie

Unscheduled visit/call

If an unscheduled visit/call is needed the unscheduled form in the eCRF must be completed.

7.3. Flow-chart

Table 4: Connection between visits and assessments

Visit (V)	V0	V1	V2
Timing of visit (weeks)	0	0	1-14 days after V0
Activity			
Introduction to investigation and review of Subject Information Form/Informed Consent Form	х		
Signed Informed Consent		Х	
Allocation of subject number		Х	
Check of in- and exclusion criteria		Х	
Pregnancy test (urine dipstick) – for subjects of childbearing potential only		х	
Baseline information		Х	
Randomization		Х	
		Х	X
		Х	Х
		Х	Х
			Х
Assessment of subject's wellbeing and compliance with CIP		Х	X
AEs/ADEs/SAEs/SADEs/DD		Х	Х
Protocol deviations		Х	Х
Complete eCRF		Х	Х
Termination form			Х

7.4. Concomitant treatment

There is no specific requirement to concomitant medication.

7.5. Case report forms

All assessments and observations throughout the investigation for each subject must be carefully recorded in the eCRF.

CRFs will be filled in by the principal investigator and/or delegated site personal, who have signed the Site Personnel Signature and Delegation List and Clinical Investigation Training Log.

The delegated site personal will be required to complete e-learning prior to system access. Delegated personal will receive credentials.

It is the responsibility of the principal investigator that all data are entered promptly and correctly.

8. Risk – benefit analysis and ethical considerations

8.1. Risk-benefit analysis of the investigational device

A risk management process has been performed in accordance with the requirements stated in ISO 14971 Application of risk management to medical devices and in accordance with internal Coloplast A/S procedures, including design verification, validated test methods, risk analysis and completion of a biological evaluation report for the investigational device.

There is a series of ISO standards "ISO 10993 - Biological Evaluation of medical devices" that dictates how to ensure that medical devices are safe and biocompatible for use in humans. For the investigational devices in CP362 we have followed this series, and performed the required testing, thus we are able to state the above. This is standard procedure for ensuring biocompatibility and safety in medical devices.

It is concluded that the investigational device is safe and biocompatible, when used according to the intended purpose of the device.

8.2. Risk-benefit for subjects participating in the clinical investigation

The clinical investigation is conducted in accordance with current law and applicable standards (see section 14). The rights, safety and well-being of human subjects shall prevail over the interest of science of society.

The study population will not include any vulnerable test subject such as children, pregnant or nursing women, or people with inability. MDR states a list of General Safety and Performance Requirements (GSPR) to be in compliance with. All GSPR are fulfilled for CP362 test catheter, except for those investigated in the clinical investigation. Relevant GSPRs for the clinical investigation can be found in Investigator's Brochure (Appendix 3). GSPR for CE-marked Peristeen Plus system are covered. Peristeen Gel is CE-marked under Medical Device Directive (MDD) under Peristeen Anal Plug certification and MDD extension (not under MDR), thus in compliance with MDD requirements.

To mitigate and reduce these risks, investigator/designees will be trained, according to the IFU, in correct handling of the investigator and comparator device. Furthermore, CP362 test catheters will be inserted by the study personnel and not the test subject. Test subjects will only use the test products for limited duration of time and under full supervision of the study personnel on site of the clinical investigation, and the test subjects will stay in hospital setting during the visit days. No test products will be handed out to the test subjects for independent use.

The transanal irrigation of subjects, with both investigational device and the comparator device will be performed by experienced HCP at investigational sites with many years of experience in conducting bowel management and with previous experience in working with clinical investigations.

The investigational setting is not expected to result in increased frequency or severity of the known risks associated with transanal irrigation. There are no direct benefits for the subjects involved; but, by participating in this investigation, the subjects will contribute with important information for developing improved solutions for bowel management that in turn may benefit individuals who are dependent on rectal catheters for bowel management. The subjects will be compensated for the time spent (see section 15).

8.3. Risk analysis for the conduct of the clinical investigation

A risk assessment of the clinical investigation will be conducted initially prior to the first subject enrolment and periodically re-assessed based on any new risks identified through the process. This assessment will be completed throughout the duration of the investigation, as defined by the investigational team. A risk-based monitoring strategy may be implemented including on-site remote, and central monitoring. Details of the strategy are defined in the monitoring plan.

8.4. Delegation of responsibility

Before initiation of the clinical investigation, sponsor must be provided with key personnel signed and dated curriculum vitae (not more than 2 years old) to verify their qualifications. Key site personnel are those, who treat or evaluate subject data in the clinical investigation. Also, the sponsor will ensure that all site personnel are trained in the investigation procedures, how to complete the eCRFs, procedure for reporting an adverse event (AE) or serious adverse event (SAE) (how, when, to whom), and who to contact in case of emergency related to the investigational device.

9. Monitoring Plan

The sponsor is responsible for ensuring appropriate monitoring of the clinical investigation activities.

The monitors will be the primary contact for the principal investigator and clinical investigation site personnel.

In this clinical investigation the sponsors CMs will be allocated as monitors. The monitoring will be conducted periodically at all sites by qualified personnel, to ensure that the investigation will comply with the approved CIP.

Monitoring activities are mandatory as per good clinical practice, however the extend and depth of these activities depend on the criticality of the clinical investigation, speed of enrolment, the experience of the clinical investigation site personnel in carrying out clinical investigations and specific study designs.

The data collected throughout the investigation and the conduct of the investigation, will be monitored according to the Monitoring Plan to ensure and verify, that the rights and well-being of the subjects are protected, that the data are accurate, complete and verifiable from source documents and that conduct of the investigation complies with the approved CIP, subsequent amendments (if any), ISO14155:2020 and the applicable regulatory requirements.

The investigator must be available for and agrees to cooperate with Coloplast A/S CMs during their visits and ensure, that they have direct access to all documents required, including directs access to subjects' files, to ensure thorough monitoring.

The investigation can be subject to internal audits, if relevant. All monitoring visits and possible audits will be followed by internal reports and corrective actions, if needed. Follow-up letters will be forwarded to sites after all visits and any findings should be addressed by the investigator or designee.

To ensure proper conduct of the investigation the following on site or as remote visits will be performed during the investigation:

- Site selection visit
- Site initiation visit
- Periodic monitoring visits
- Close out visit.

9.1. Site selection visit

The feasibility of the requirements and qualifications of PI and investigational site shall be verified and documented as part of the site selection process. A site selection visit can be replaced by one or more phone calls if the sponsor has prior experience working with the PI or investigational site.

9.2. Initiation visit

All clinical investigation sites will complete an initiation visit during which full training on all aspects of the clinical investigation will be provided.

Training in use of the equipment used for measuring the assessment related to the secondary objective will be performed at sites.

9.3. Monitoring visit(s)

The site dedicated monitor is to ensure adherence to the clinical investigation plan, the safety of the subjects, accurate data recording on the e-CRFs and to monitor recruitment rates and adherence to follow-up schedules. During the clinical investigation, monitors shall check that appropriate written informed consents have been obtained. The PI shall permit and assist the monitor to carry out verification of completed eCRFs against data in the source documents.

The sponsor shall determine the extent and nature of monitoring appropriate for the clinical investigation based on the risk assessment. The sponsor shall ensure, through oversight of the clinical investigation and timely adverse event reporting, that unanticipated adverse device effects are identified and investigated rapidly so that, where necessary, additional risk control measures can be implemented.

The PI can delegate tasks to his/her collaborators, however the roles and responsibilities as time of involvement for each clinical site personnel must be documented on the Site Personnel signature and Delegation list as well as training received before getting involved with the clinical investigation must be documented in the Clinical Investigation Training Log.

The monitor shall inform the sponsor about any problems relating to facilities, technical equipment, or personnel at the clinical investigation site. The monitor shall also be responsible for notifying such deficiencies in writing to the PI and convene with the clinical investigation site personnel appropriate and timely corrective actions.

The sponsor, or delegate, will provide clinical monitoring, including review of eCRF with verification to the source documentation, as described below:

- All available data in the eCRF must be monitored including verification of all fields in the eCRF.
- Within 4 weeks after a subject has completed/terminated the investigation, all data should be monitored and all queries related to the subject must be resolved and closed Fourteen days before planned LPO, the monitoring and verification of all available data in the eCRF must be finalised and all available queries must be resolved and closed.
- For subjects terminating the investigation within 14 days before planned LPO, monitoring and verification of data must be finalized within 2 days after the subject's termination visit.
- After LPO, monitoring and verification of data must be finalized within two days after LPO.
- Queries raised after LPO must be resolved within two days.
- At the Monitoring Visits before the planned LPO, the monitor must ensure PI readiness for signing the eCRF (has completed relevant eLearning in the eCRF) and is available for signature after LPO. In addition, ensure site personnel is available for query resolution after LPO, if raised.

The monitor shall make written reports to the sponsor, including documentation of any deviations after each visit. Follow-up letters will be forwarded to sites after all visits and any findings should be addressed by the PI or designee.

9.4. Remote monitoring

Remote (source data verification) and/or centralized (data review) monitoring is carried out by sponsor personnel or representatives (e.g., data management personnel, statisticians, or clinical monitors) at a location other than the site(s) at which the clinical investigation is being conducted (evaluation without visiting the investigation site). Remote monitoring processes can provide many of the capabilities of on-site monitoring as well as additional capabilities.

In addition to onsite monitoring visits, remote monitoring of the data entered in the eCRF system could be used to achieve the following:

- Conduct activities such as: standard checks of range, consistency, and completeness of data and checks for unusual distribution of data, such as too little variance).
- Special attention will be given in case of frequent data anomalies or errors, protocol deviations or excessive dropouts.
- Augment on-site monitoring by performing monitoring activities that can only be accomplished using centralized processes (e.g., statistical analyses to identify data trends not easily detected by on-site monitoring).
- Monitor data quality through routine review of submitted data in real-time to identify missing data, inconsistent data, data outliers, and potential protocol deviations that may be indicative of systemic and/or significant errors in data collection and reporting at the site.
- Verify source data remotely, provided that both source data and CRFs can be accessed remotely.
- Conduct aggregate statistical analyses of investigational data to identify subject data that are outliers
 relative to others and to evaluate individual subject data for plausibility and completeness.
- Conduct analyses of site characteristics, performance metrics (e.g., high screen failure rates, high frequency of eligibility deviations, and delays in reporting data), and clinical data to identify early on corrective actions needed for characteristics correlated with poor performance or noncompliance.

9.5. Source data verification

Source data is all information in original records, certified copies of original records of clinical findings, observations, or other activities in the clinical investigation, necessary for the reconstruction and evaluation of the clinical investigation. This includes source data initially recorded in an electronic format.

All documents and data related to the clinical investigation handled by site personnel, shall be produced, and maintained in a way that assures reliability, integrity, control, and traceability, and shall be appropriately stored to provide a complete history.

The PI shall assure the accuracy, attribution, completeness, legibility, and timeliness of the data reported to the sponsor in the eCRFs and in all required reports. All printed copies of electronic source documents shall be certified, as indicated by a dated signature by the investigational site personnel at the time the document is printed. Special requirements should be applied to the capture, review, and retention of electronic source data, to ensure reliability, quality, integrity, and traceability.

The data reported in the eCRFs shall be derived from source documents and be consistent with these source documents, and any discrepancies shall be explained in writing. The eCRF can serve as the source document and this must be documented on the Source Data Specification Form. The Source Data Specification Form must be completed at the initiation visit detailing the location of the source data for each data point agreed upon by the PI. Only the PI, relevant site personnel, and the sponsor representatives will have access to all the eCRFs.

10. Statistical considerations

10.1. Statistical design, method and analytical procedures

Definition of analysis populations:

Intention to Treat (ITT) and Safety populations will be defined at a formal data review meeting before database lock. As a minimum, the data manager, the clinical manager and the statistician will be involved in the classification of subjects.

The ITT population (full analysis set) will be constituted by all subjects with valid informed consent who have been exposed to at least one Test product, with information on at least one endpoint or assessments used to evaluate the primary or secondary objective.

The Safety population will constitute by subjects who have given informed consent.

All evaluations of endpoint and assessments will be based upon the ITT population whereas adverse events and device deficiencies will be assessed based on the safety population. Invalid individual data points may be omitted from evaluations even though the corresponding subject is part of the ITT population. Any exclusion of data points will be documented.

Considering the data obtained it might be considered to make additional explorative analyses based on a subset of the ITT population.

Evaluation of endpoints and assessments:

All baseline measurements, endpoint and assessments will be summarized by descriptive statistics and/or listed. Endpoint and assessments will be summarized by product, if relevant.

Descriptive statistics for continuous variables are presented with N, Mean, SD (standard deviation), Median, Min and Max, where N denotes the number of subjects contributing with non-missing data. For discrete variables, descriptive statistics are presented with N and percentage, where percentage is based on the total number of subjects/observations with non-missing data.

As an exploratory analysis to support the aim of the investigation the proportion of successful irrigations will be compared for the two type of devices by a one-sided Fisher's Exact Test testing if the proportion with the investigational device is lower than with the Comparator device. The test will be performed on a 5% test level.

Other summaries and analyses can be made, if relevant.

As it is an exploratory clinical investigation no adjustment for multiple testing will be applied if statistical analyses are performed.

All statistical analyses and summaries are made with SAS version 9.4 (SAS Institute Inc., Cary, NC) /Enterprise Guide version 7.1.

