5.4. Rationale for selection and measurement of endpoints

The endpoints and assessment have been selected to support the aim of the investigation exploring the feasibility of performing TAI with the investigational device.

The primary endpoint has been selected to evaluate if it is feasible to use investigational device for TAI to fulfil its intended purpose. Irrigation is defined according to the IFU and must be done with the regular volume of water used by the subject.

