5.8. Blinding

Subjects and HCP will not be blinded in this investigation. Furthermore, since this is an exploratory investigation, Coloplast A/S personnel (e.g., CMs, Data Management Specialist, Biostatistican) will also not be blinded.

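### Could the undefined term 'invalid' in section 10.1 let failed irrigations drop out of the primary success proportion?

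*Combined protocol and SAP*

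**What the plan says.** The omission rule is in section 10.1: "Invalid individual data points may be omitted from evaluations even though the corresponding subject is part of the ITT population". It is followed by one safeguard: "Any exclusion of data points will be documented". For discrete variables, the same section says the "percentage is based on the total number of subjects/observations with non-missing data".

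The analysis populations are settled at a pre-lock meeting, and section 10.1 says who takes part: "As a minimum, the data manager, the clinical manager and the statistician will be involved in the classification of subjects". Section 5.8 leaves the sponsor's staff open to allocation: "Coloplast A/S personnel (e.g., CMs, Data Management Specialist, Biostatistican) will also not be blinded". Section 9.4 lists possible uses of remote monitoring, among them: "Monitor data quality through routine review of submitted data in real-time to identify missing data, inconsistent data, data outliers".

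The primary endpoint (section 5.2) is a Yes/No answer, given after each of the two visits, on whether transanal irrigation could be performed. Section 5.4 says what counts: "Irrigation is defined according to the IFU and must be done with the regular volume of water used by the subject". Section 10.1 plans an exploratory one-sided Fisher's exact test at 5%, asking whether the success proportion is lower with the investigational catheter. Section 10.4 sets no success criterion.

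**The concern.** The main result is a single proportion on about 20 irrigations per device, so each value counts. Three features together look risky.

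- The rule that allows omission has no criterion and covers every variable, the primary endpoint included.
- An omitted value leaves both numerator and denominator, so dropping a failure always raises the success proportion.
- The people who handle the data know the device and can see the outcome before lock.

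The volume condition in section 5.4 adds to the doubt. An irrigation stopped early could be called a failure. It could also be called not an irrigation in the defined sense, and so invalid. A malfunction or use error might well cause such a stop, and a first-in-human feasibility study should count it. Every omitted investigational failure also raises the Fisher p-value, so the error would always favour the new device.

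**Working it through.** **Step 1: does the plan, followed as written, remove failures?**

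- Section 5.2 asks whether irrigation was possible. 'No' is one of its two permitted answers.
- Section 5.4 defines irrigation by the IFU and the subject's usual volume. An attempt that does not reach that definition answers the section 5.2 question with 'No'.
- Section 10.1 concerns invalid data points. A recorded and verified 'No' is valid, and nothing in section 10.1 equates failure with invalidity.
- The meeting in section 10.1 is described as classifying subjects. Section 9.4 is about finding data errors. Neither authorises dropping an outcome.

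So the ordinary reading keeps failed attempts in the denominator. The concern needs an extra step, re-labelling, that no section calls for.

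**Step 2: how large would the effect be if it happened?**

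The plan gives no expected rates, power or margin, so there is no figure to reproduce. From the plan: up to 20 irrigations per device (20 randomised, crossover), and a one-sided Fisher test at 5% that treats the two sets as independent. Assumed: f = 1 to 10 investigational failures, k = 0, 1 or 2 of them omitted (k no larger than f), and comparator successes of 20, 19 or 18 out of 20.

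*Proportion.* With s = 20 − f successes, the first omission adds s/19 − s/20 = s/380.

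- f = 1: 19/380 = 5.0 points (95.0% to 100%)
- f = 5: 15/380 = 3.9 points (75.0% to 78.9%)
- f = 10: 10/380 = 2.6 points (50.0% to 52.6%)

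If both of two failures were dropped, 18/20 (90%, exact 95% CI 68.3 to 98.8) would become 18/18 (100%, CI 81.5 to 100).

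*Fisher test.* The p-value is the hypergeometric probability of s or fewer investigational successes. With a 20/20 comparator and 5 failures, all failures lie on one side:

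- k = 0: C(20,5)/C(40,5) = 15504/658008 = 0.0236
- k = 1: C(19,4)/C(39,4) = 3876/82251 = 0.0471
- k = 2: C(18,3)/C(38,3) = 816/8436 = 0.0967

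Over the 3 × 10 = 30 combinations, these are the only ones where p moves from at or below 0.05 to above it:

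| Comparator | Failures of 20 | k = 0 | k = 1 | k = 2 |
|---|---|---|---|---|
| 20/20 | 5 | 0.0236 | 0.0471 | 0.0967 |
| 19/20 | 6 | 0.0457 | 0.0796 | 0.1390 |
| 19/20 | 7 | 0.0218 | 0.0386 | 0.0688 |
| 18/20 | 8 | 0.0324 | 0.0527 | 0.0860 |

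Two of the four need both omissions. All four need 5 to 8 failures in 20, and a success rate of 60% to 75% would be plain to any reader whatever the p-value.

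**Step 3: would an omission be visible?**

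All eCRF fields are verified (section 9.3), and discrepancies with source must be explained in writing (section 9.5). The PI signs each eCRF and the system keeps an audit trail (section 11). Section 10.1 requires exclusions to be documented, and the report must critically evaluate all the data collected (section 18). Malfunctions and use errors count as device deficiencies (section 16.3), which section 10.1 assesses on the safety population. A device-caused failure recorded as a deficiency would thus still be reported if its endpoint value were dropped.

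**The case for a change.** The best case for a change is that documentation comes after the fact. It shows that a value was dropped, but it neither sets a rule in advance nor corrects the headline percentage. With no pass/fail threshold, readers rely on that percentage, and a one-line definition would cost almost nothing.

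Part of this stands. The term is undefined in the text available, and the primary endpoint is not expressly protected. The Data Validation Plan (section 11) is described as covering edit, range and consistency checks, which is not the same as a coding rule for stopped attempts.

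The rest is weaker. The argument depends on staff treating a verified failure as bad data, against the natural reading of sections 5.2 and 5.4. Open allocation adds little, because a reviewer blinded to device would still see the Yes or No. A definition would not remove judgement either: a stop for reasons unrelated to the procedure would still have to be coded one way or the other. The absence of a rule is also uncertain. Parts of section 5 and of the visit 1 steps are blank in the public text, and the IFU and the Data Validation Plan are not included. Any of these may hold the rule.

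**Conclusion.** No change follows. The plan leaves 'invalid' undefined, but a statistician following sections 5.2, 5.4 and 10.1 would count a failed attempt as 'No', keep it in the denominator, and reserve omission for values that are really in error. That gives a sound proportion.

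If one failure were wrongly dropped, the proportion would rise by 2.6 to 5.0 points for 1 to 10 failures in 20. With up to two dropped, the Fisher result would change in 4 of the 30 assumed combinations. These sizes rest on assumed counts and on 20 irrigations per device. The test is exploratory, section 10.4 sets no success criterion, and section 2 says the data will not be used for conformity assessment. The possible harm is a somewhat flattering feasibility estimate, and it would come from a documented departure from the ordinary reading of the plan.
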